Indication:	
ENSEAL X1
 
The ENSEAL X1 devices are bipolar electrosurgical instruments for use with an electrosurgical generator. They are intended for use during open or laparoscopic surgical procedures to cut and seal vessels, and to cut, grasp and dissect tissue during surgery.
 
Indications for use include open and laparoscopic general, gynecological, urologic, thoracic, and ear, nose, and throat (ENT) surgical procedures or any procedure where vessel ligation (cutting and sealing), tissue grasping, dissection, and division of vessels, lymphatics, and tissue bundles is performed (e.g. bowel resections, hysterectomies, gall bladder procedures, Nissen Fundoplication, adhesiolysis, and oophorectomies). The devices can be used on vessels up to and including 7 mm and bundles as large as will fit in the jaws of the instruments.
 
The ENSEAL X1 Tissue Sealers have not been shown to be effective for tubal sterilization or tubal coagulation for sterilization procedures.
 
GEN11
 
The GEN11 provides radiofrequency power to drive ENSEAL electrosurgical instruments that are used during open or laparoscopic general and gynecological surgery to cut and seal vessels and to cut, grasp, and dissect tissues. In addition, the generator provides power to drive HARMONIC ultrasonic surgical instruments that are indicated for soft tissue incisions when bleeding control and minimal thermal injury are desired.
 
ENSEAL and HARMONIC instruments, when used with the GEN11, have not been shown to be effective for sterilization procedures or tubal coagulation.

Objective(s):	
The primary objective of this study is to demonstrate the acceptable performance and safety of the ENSEAL X1 and GEN11 devices when used per the instructions for use (IFU).

Overview of Study Design:	
This prospective, single-arm, multi-center study will collect clinical data in a post-market setting by procedure group (thoracic, urologic, and ENT). Investigators will perform each procedure using the device in compliance with their standard surgical approach and the ENSEAL X1 and GEN11 IFUs.
 
Subjects will be consented and screened anytime during a period of 8 weeks prior to the date of surgery. Subjects will be considered enrolled when the ENSEAL X1 device has been attempted to be used for a vessel transection during thoracic, urologic, or ENT procedures. All enrolled

	subjects will be followed post-operatively through discharge and again at 28 days (\pm 14 days) post-surgery; therefore, from the surgery date to study exit, the duration will be approximately 6 weeks.
Number of Subjects:	A minimum of 105 subjects enrolled (maximum of 120 subjects enrolled) will be included in the study from up to 12 surgery centers globally with the following procedure targets: 
 • A minimum of 35 subjects enrolled to a maximum of 40 subjects enrolled for thoracic procedures (e.g., lung resections [branches, no pulmonary artery/pulmonary vein {PA/PV}]); • A minimum of 35 subjects enrolled to a maximum of 40 subjects enrolled for urologic procedures (e.g., nephrectomy); and • A minimum of 35 subjects enrolled to a maximum of 40 subjects enrolled for ENT procedures (e.g., thyroidectomy, tonsillectomy, parotidectomy, radical neck).
Criteria for Inclusion:	Subjects satisfying the following criteria will be considered eligible for enrollment in this study: 
 1. Primary laparoscopic or open procedure (thoracic, urologic, or ENT) where at least one vessel is planned to be transected by the ENSEAL X1 device per the IFU; 2. Willingness to give consent and comply with all study-related evaluations and visit schedule; and 3. At least 18 years of age.
Criteria for Exclusion:	Subjects meeting any of the following criteria will be considered ineligible for enrollment in this study: 
 1. Physical or psychological condition which would impair study participation; or 2. Enrollment in a concurrent interventional clinical study that could impact the study endpoints.
Test Product:	ENSEAL® X1 Curved Jaw Tissue Sealer (Product Codes: NSLX125C, NSLX137C, or NSLX145C) and Generator G11 (GEN11).
Reference Therapy/Product:	No comparator product is being used in this study.
Duration of Treatment:	Subjects will be exposed to the ENSEAL X1 device during the procedure and while the device is used as indicated in the IFU. The device nor any device components remain in the patient after use.
Criteria for Evaluation:	The primary performance endpoint will be: 
 • The number and percentage of vessels where hemostasis is achieved (\leq Grade 3) per the grading scale below: 
 ○ Grade 1: no bleeding at transection site;

	
 ○ Grade 2: minor bleeding at transection site, no intervention needed; ○ Grade 3: minor bleeding at transection site, mild intervention needed, use of compression, basic energy devices (monopolar and/or bipolar) and/or touch-ups with ENSEAL X1; or ○ Grade 4: significant bleeding (e.g., pulsatile blood flow, venous pooling) requiring intervention such as extensive coagulation or use of additional hemostatic measures (e.g., hemoclips, staples, sutures, fibrin sealants, other advanced energy products); 
The secondary performance endpoints will be:
 
 • Distribution of 5-point scale scores for various tasks completed by the ENSEAL X1 device (adhesiolysis, lymphatics or tissue bundles divided, tissue grasping, tissue cutting, or tissue dissection); • Distribution of hemostasis grading scale (1-4) for each vessel transected; and • Type, name, and number of additional hemostasis measures required to achieved hemostasis for Grade 4 vessel transections. 
The safety endpoint will be:
 
 • Occurrence of device-related (possibly, probably, or causally) adverse events (AEs).
Statistical Analysis:	
Analysis Sets
 
The summary of all performance and safety endpoints will be performed on the set of subjects in whom the ENSEAL X1 device is utilized during the surgical procedure. The summary of all performance and safety endpoints will be performed by procedure group and on the entire pooled set of subjects.
 
Sample Size Determination
 
A sample size of 105 to 120 treated subjects is planned for enrollment in this study. No formal hypothesis is being tested in this study, thus the sample size was not statistically sized, but rather is considered sufficient for a descriptive summary of performance endpoints within each procedure group. It is expected that at least 1 vessel will be transected within each procedure, providing an expected minimum of at least 35 transections within each procedure group for a total of at least 105 transections.
 
From a safety perspective on the pooled analysis of 105 subjects and in consideration of rare AEs that may occur (e.g., bleeding requiring blood product transfusion), for an event that has an incidence rate of, for example, 2%, then in a sample of 105 subjects, the probability of observing at least 1 event is 88.0% under a binomial probability model. Thus, this sample size provides a high probability of observing rare events if they do occur, and provides reasonable assurance to conclude

that the likelihood of such AEs is less than 3.5% if they do not occur based on the upper limit of an exact 95% confidence interval when 0 events out of 105 subjects are observed.

Performance Analyses

The number and percentage of vessels where hemostasis is achieved (\leq Grade 3) will be summarized and an exact 95% confidence interval will be estimated for each procedure group (thoracic, urologic and ENT) and in total. Counts and percentages will be provided for type, size, and number of vessels transected, grading scale distribution for all vessels transected, number of times ENSEAL X1 touch-ups were required, and incidence of requirement for additional measures to obtain hemostasis on vessels.

Safety Analyses

Participating investigators will ensure that this protocol, Informed Consent Document (ICD), ICD or protocol amendments, and if applicable, any other written information provided to the subjects that assist in the decision to participate are reviewed by an Institutional Review Board (IRB) or Ethics Committee (EC) that complies with governmental requirements. The approving IRB/EC will be responsible for the initial and continuing review and approval of this clinical investigation. Participating investigators will be required to promptly report to the IRB/EC as required by the IRB/EC's policies. Additionally, investigators will be required to refrain from making any changes in the clinical investigation plan without Sponsor and IRB/EC approval of an amended protocol, except where necessary to eliminate apparent immediate hazards to study subjects or others.

Applicable Regulations

This study will be conducted in compliance with GCP and in accordance with the Declaration of Helsinki, as well as any other applicable local and country regulatory requirements.

Subject Information and Consent

Regulations concerning the protection of subjects require that informed consent be obtained before a subject may participate in any clinical investigation. An IRB/EC approved informed consent must be sought from each subject and must be appropriately documented in the subject's medical record prior to initiating the study. It is the Investigator's responsibility to obtain written informed consent from the subject, the Investigator may delegate this responsibility if appropriately documented.

The informed consent process involves the following: giving a subject adequate information concerning the study, providing adequate time for the subject to consider all available options, responding to the subject's questions, ensuring that the subject has comprehended this information and finally, obtaining the subject's written consent to participate in this study. All subjects in this study should be completely informed about the purpose, risks, benefits, and other pertinent details of this study. The informed consent process is careful to avoid the perception of any coercion or undue influence on, or inducement of, the subject to participate, and does not waive or appear to waive the subject's legal rights. The ICD is presented in native, non-technical language that is understandable to the subject.

Prior to a subject's participation in this study, an ICD will be signed and dated by the subject and person who conducted the consent discussion. The subject will be provided a copy of the signed ICD. The ICD and any other written materials provided to the subject to assist in the decision to participate must be revised whenever new information becomes available that may be relevant to their willingness to participate or continue participation in this study. Revision to the ICD and other written materials will receive IRB/EC approval before implementation. Each subject will be required to sign any amended ICD (as required by the IRB/EC) and will receive a copy of the signed ICD.

ADMINISTRATIVE REQUIREMENTS

This study is sponsored by Ethicon Endo-Surgery, Inc. (EES, Cincinnati, OH, USA) and will be conducted in up to twelve surgery centers globally under a single protocol approved by each participating site's IRB/EC prior to implementation. The principal investigator at each study site is a surgeon qualified by education, experience, and training to perform the study procedure and to assume responsibility for the conduct of this study.

The Data Management and Biostatistics groups of the Sponsor will be responsible for the analysis of data from this protocol. An Electronic Data Capture (EDC) system will be utilized by study site personnel to transfer study data from source records (the first point of clinical data capture) onto common electronic case report forms (eCRFs).

Protocol Modifications

All protocol amendments must be issued by the Sponsor, signed and dated by the Investigator, and should not be implemented without prior IRB/EC approval, except where necessary to eliminate immediate hazards to the subjects or when the change(s) involves only logistical or administrative aspects of the study (e.g., change in monitor(s), change of telephone number(s)). The Investigator reports the protocol amendments to the IRB/EC as per their local requirements.

1.0 INTRODUCTION

The ENSEAL X1 devices are a sterile, single-patient-use advanced bipolar surgical instrument intended for use during open or laparoscopic surgical procedures to seal and transect vessels up to and including 7mm in diameter, and to cut, grasp and dissect tissue during surgery.

ENSEAL X1 devices differ primarily in three ways from the earlier version of the device, the ENSEAL® G2 Tissue Sealer (ENSEAL G2).

1. The ENSEAL G2 relied on I-BLADE® Technology to provide compression along the device tip, whereas the ENSEAL X1 has a redesigned jaw that provides uniform compression without the need for an I-BLADE.
2. The ENSEAL G2 used a positive temperature coefficient technology to modulate energy flow and control temperature at the blade, whereas ENSEAL X1 uses electrical impedance feedback to intelligently monitor tissue conditions and modulate energy delivery to ensure effective sealing while minimizing tissue damage.
3. The ENSEAL G2 had an integrated seal-and-cut steps for use, whereas ENSEAL X1 has separated these into intuitive, simplified functions, so that surgeons may now seal without cutting, cut without sealing, or both seal and cut.

The ENSEAL X1 devices have undergone extensive preclinical testing to ensure that they are capable of producing strong and durable seals for vessels up to 7mm in diameter. Beginning in 2018, the open-surgery version, ENSEAL X1 Large Jaw, was successfully launched. Now, a laparoscopic version, ENSEAL X1 Curved Jaw (Figure 1) is being introduced to the market. With a shaft diameter of 5 mm, the device will be available in lengths of 25, 37, and 45 cm. The curved tapered tip of the device is designed for fine dissection, while being able to capture more tissue per bite with stronger grasping than the predicate ENSEAL G2 device. The shaft can be rotated a full 360° for easier access to targeted tissue.

[figure not shown]

Figure 1: Image of the ENSEAL X1.

The GEN11 supplies energy to the HARMONIC and ENSEAL surgical instruments. It also has a touchscreen for easy setup and operation, and a high-resolution display with wider viewing angles. Software updates to ensure that the system is operating optimally are available via USB memory stick. The generator has a unique receptacle port that accepts either a HARMONIC or

an ENSEAL instrument. Connectors (HGA11 for HARMONIC and EGA11 for ENSEAL) are used to enable the generator to power legacy instruments.

The ENSEAL X1 devices include several incremental enhancements of the same basic technology used with predicate ENSEAL G2 devices. This study is being initiated to evaluate the ENSEAL X1 device when used per their instructions for use (IFU) in the following types of procedures: thoracic, urologic, and ENT.

2.0 STUDY OBJECTIVES

The primary objective of this study is to demonstrate the acceptable performance and safety of the ENSEAL X1 and GEN11 devices when used per the instructions for use (IFU).

2.1 PRIMARY PERFORMANCE ENDPOINT

A hemostasis grading scale was adapted from Siegel et al.¹ The primary performance endpoint will be:

- The number and percentage of vessels where hemostasis is achieved (\leq Grade 3) per the grading scale below:
 - Grade 1: no bleeding at transection site;
 - Grade 2: minor bleeding at transection site, no intervention needed;
 - Grade 3: minor bleeding at transection site, mild intervention needed, use of compression, basic energy devices (monopolar and/or bipolar) and/or touch-ups with ENSEAL X1; or
 - Grade 4: significant bleeding (e.g., pulsatile blood flow, venous pooling) requiring intervention such as extensive coagulation or use of additional hemostatic measures (e.g., hemoclips, staples, sutures, fibrin sealants, other advanced energy products).

2.2 SECONDARY PERFORMANCE ENDPOINTS

The secondary performance endpoints will be:

- Distribution of 5-point scale scores for various tasks completed by the ENSEAL X1 device (adhesiolysis, lymphatics or tissue bundles divided, tissue grasping, tissue cutting, or tissue dissection). The scale will be a 5-point scale (very dissatisfied, dissatisfied, neither satisfied or dissatisfied, satisfied, or very satisfied) asking how satisfied the surgeon was with the use of the device for each of the tasks;
- Distribution of hemostasis grading scale (1-4) for each vessel transected; and
- Type, name, and number of additional hemostasis measures required to achieve hemostasis for Grade 4 vessel transections.

2.3 SAFETY ENDPOINT

The safety endpoint will be occurrence of device-related (possibly, probably, or causally) adverse events (AEs).

2.4 ADDITIONAL KEY DATA COLLECTED

Additional key data collected for evaluation in this study are:

- Procedure duration;

- Use of any other energy device (basic [monopolar and traditional bipolar], advanced bipolar, ultrasonic) in primary procedure (type, name, and number of device and reason for use), if applicable;
- Surgeon questionnaire administered once per investigator;
- Generator questionnaire after each procedure for each GEN11 used;
- Surgical procedure conducted;
- Hospital stay duration;
- Name and number of vessels that were transected, surgeon determination of diameter size range (< 3 mm, 3 to 5 mm, and > 5 to 7 mm);
- Occurrence and location of cancer and occurrence of pre-surgical radiation/chemotherapy within 90 days prior to surgery, if applicable;
- Occurrence of vessel skeletonization;
- Presence of inflamed tissue, calcified tissues/vessels, atherosclerotic tissue, fibrotic tissue, or presence of adhesions intraoperatively, if applicable;
- Volume of estimated intra-operative blood loss;
- Occurrence of blood transfusion, if applicable (record the total required units of blood and rationale);
- Type of additional mild interventions (use of compression, basic energy devices [monopolar and/or bipolar] and/or touch-ups with ENSEAL X1) required to achieve hemostasis for Grade 3 vessel transections including number of times when ENSEAL X1 touch-ups were used; and
- Procedure-related AEs.

3.0 INVESTIGATIONAL PLAN

3.1 OVERALL STUDY DESIGN AND PLAN - DESCRIPTION

This prospective, single-arm, multi-center study will collect clinical data in a post-market setting by procedure group (thoracic, urologic, and ENT). Investigators will perform each procedure using the device in compliance with their standard surgical approach and the ENSEAL X1 and GEN11 IFUs.

Subjects will be consented and screened anytime during a period of 8 weeks prior to the date of surgery. Subjects will be considered enrolled when the ENSEAL X1 device has been attempted to be used for a vessel transection during thoracic, urologic, or ENT procedures. All subjects enrolled will be followed post-operatively through discharge and again at 28 days (\pm 14 days) post-surgery; therefore, from the surgery date to study exit, the duration will be approximately 6 weeks.

3.2 STUDY POPULATION

3.2.1 Enrollment

Subjects will be recruited from the existing patient population who plan to have a procedure from the proposed procedure groups (thoracic, urologic, and ENT) utilizing consecutive screening and enrollment in an effort to generate a random and representative patient population sample. All eligible subjects (Sections 3.2.3 and 3.2.4) will be considered enrolled at the time when the ENSEAL X1 device has been attempted to be used for a vessel transection during one of the proposed procedure groups. Up to 12 surgery centers globally will be selected as study sites. Each participating investigator is

expected to perform a minimum of two procedures using the ENSEAL X1 device. A minimum of 105 subjects enrolled (maximum of 120 subjects enrolled) will be included in the study with the following procedure targets:

- A minimum of 35 subjects enrolled to a maximum of 40 subjects enrolled for thoracic procedures (e.g., lung resections [branches, no PA/PV]);
- A minimum of 35 subjects enrolled to a maximum of 40 subjects enrolled for urologic procedures (e.g., nephrectomy); and
- A minimum of 35 subjects enrolled to a maximum of 40 subjects enrolled for ENT procedures (e.g., thyroidectomy, tonsillectomy, parotidectomy, radical neck).

3.2.2 Screening Failures

All subjects signing consent who do not have at least one vessel transection attempted by ENSEAL X1 during their procedures will be recorded as screen failures. For subjects who are determined to be screen failures, only the relevant eCRF pages (inclusion/exclusion criteria, demographics, AEs, subject completion/discontinuation) will be completed.

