3.4.2 Surgical Variables

The following variables will be recorded preoperatively, intraoperatively, or postoperatively:

- Date/time of hospital admission;
- Body weight (kg or lbs; no shoes);
- Body height (cm or in; no shoes);
- Procedure duration, defined as first skin incision to final skin closure;
- Did vessel skeletonization occur (Yes/No; if Yes, describe vessel skeletonized and device used)?;
- Was there presence of inflamed tissue, calcified tissues/vessels, atherosclerotic tissue, fibrotic tissue, or presence of adhesions intraoperatively, if applicable (Yes/No; if Yes, describe the tissue along with location)?;
- Were adhesions removed or divided by ENSEAL X1 (Yes/No; if Yes, describe adhesions along with location and complete 5-point scale)?;
- Were lymphatics and tissue bundles divided by ENSEAL X1 (Yes/No; if Yes, describe lymphatics and tissue bundles along with location and complete 5-point scale)?;
- Was ENSEAL X1 used for grasping tissue, tissue cutting, or tissue dissection (Yes/No; if Yes, describe activity along with location and complete 5-point scale)?;

- Conversion to open with reason, if applicable;
- Volume of estimated intra-operative blood loss;
- Use of any other energy device (monopolar, traditional bipolar, advanced bipolar, ultrasonic) in primary procedure (type, name, and number of device and reason for use), if applicable;
- Name, product code, and number of Ethicon trocars used with ENSEAL X1; if applicable;
- Type and name of trocar used with ENSEAL X1 device, if applicable;
- Was there prophylactic use of clips as standard of surgical care before vessel transection (Yes/No; if Yes, name vessel transected, and number of clips prophylactically applied);
- For each vessel transected with ENSEAL X1:
 - Name of each vessel;
 - Hemostasis grading scale assessment (1-4);
 - Surgeon determination of diameter size range (< 3 mm, 3 to 5 mm, and > 5 to 7 mm);
 - Image captured where the vessel is perpendicular and below the open jaw of the ENSEAL X1 device;
 - For every Grade 3 vessel transection:
 - Compression used as a mild intervention, if applicable (Yes/No);
 - Touch-ups with a monopolar device, if applicable (Yes/No; if Yes, record number of touch-ups);
 - Touch-ups with a bipolar device, if applicable (Yes/No; if Yes, record number of touch-ups);
 - Touch-ups with ENSEAL X1 (Yes/No; if Yes, record number of touch-ups);
 - For every Grade 4 vessel transection intervention:

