5.6 ANALYSIS SETS

The summary of all performance and safety endpoints will be performed on the set of subjects in whom the ENSEAL X1 device is utilized during the surgical procedure. The summary of all performance and safety endpoints will be performed by procedure group and on the entire pooled set of subjects.

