5 Levels of Significance

No hypotheses are specified for this study and no p-values are being calculated, therefore no level of significance is specified. All estimation of endpoints will be performed using 95% confidence intervals.

6 Analysis Sets

The summary of all performance and safety endpoints will be performed on the set of subjects in whom the ENSEAL X1 device is utilized during the surgical procedure. This will be labeled the ENSEAL Analysis Set. This set of subjects will be identified by having at least one entry in the “Vessel Transected” eCRF or by having answered “Yes” to the question “Was ENSEAL X1 used for tissue cutting or dissection?” on the “ENSEAL X1 Usage” eCRF. The summary of all primary and secondary performance endpoints will be performed by procedure group (thoracic, urologic, and ENT) and on the entire pooled set of subjects. The safety endpoints will be summarized by procedure group and for the entire pooled set of subjects.

7 Sample Size Justification

A sample size of 105 to 120 treated subjects is planned for enrollment in this study. No formal hypothesis is being tested in this study; thus, the sample size was not statistically sized, but rather is considered sufficient for a descriptive summary of performance endpoints within each procedure group. It is expected that at least 1 vessel will be transected within each procedure, providing an expected minimum of at least 35 transections within each procedure group for a total of at least 105 transections.

From a safety perspective on the pooled analysis of 105 subjects and in consideration of rare AEs that may occur (e.g., bleeding requiring blood product transfusion), for an event that has an incidence rate of, for example, 2%, then in a sample of 105 subjects, the probability of observing at least 1 event is 88.0% under a binomial probability model. Thus, this sample size provides a high probability of observing an AE if they do occur and provides reasonable assurance to conclude that

the likelihood of such AEs is less than 3.5% if they do not occur based on the upper limit of an exact 95% confidence interval when 0 events out of 105 subjects are observed.

8 Analyses to be Conducted

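### Subjects in whom ENSEAL X1 is used without a vessel attempt become screen failures, although the safety set is defined by device use: Protocol 3.2.2 and 5.6 and SAP 6 and 8.7 do not fit together

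*Protocol*

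**What the plan says.** **Enrolment and follow-up.** Protocol 3.1: "Subjects will be considered enrolled when the ENSEAL X1 device has been attempted to be used for a vessel transection". The same section states: "All subjects enrolled will be followed post-operatively through discharge and again at 28 days".

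**Screen failures.** Protocol 3.2.2 applies to subjects who signed consent and "who do not have at least one vessel transection attempted by ENSEAL X1 during their procedures will be recorded as screen failures". For them, "only the relevant eCRF pages (inclusion/exclusion criteria, demographics, AEs, subject completion/discontinuation) will be completed". The AE page is on that list. The ENSEAL X1 Usage, intra-operative and discharge pages are not.

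**Non-vessel uses.** Protocol 2.2 makes surgeon satisfaction with these tasks a secondary endpoint: "adhesiolysis, lymphatics or tissue bundles divided, tissue grasping, tissue cutting, or tissue dissection". Protocol 3.4.2 asks "Was ENSEAL X1 used for grasping tissue, tissue cutting, or tissue dissection", with separate items for adhesions and for lymphatics and tissue bundles. Under Protocol 2.3 the safety endpoint is device-related AEs.

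**Who is analysed.** Protocol 5.6 takes "the set of subjects in whom the ENSEAL X1 device is utilized during the surgical procedure" for performance and safety alike. SAP 6 names this the ENSEAL Analysis Set and identifies members in one of two ways: an entry on the vessel form, or a Yes to "Was ENSEAL X1 used for tissue cutting or dissection" on the Usage form. SAP 8.7 restricts every summary to enrolled subjects. SAP Tables 8 (usage and satisfaction) and 14 to 19 (AEs) are on the ENSEAL Analysis Set. Listing 24 gives AEs for all subjects. SAP Table 1 has a row for screen failures that arise intra-operatively.

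**The concern.** Take a consented subject for whom an X1 vessel transection was planned. The surgeon dissects and divides tissue bundles with X1 but takes every vessel by other means. That subject has been exposed to the device in a way that the endpoints and Protocol 5.6 cover. The enrolment rule nevertheless turns the subject into a screen failure, and the form that would show the exposure is not completed. The analysis set then depends on data that the protocol does not collect.

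Two things are at stake. One is complete ascertainment of late device-related AEs in everyone exposed. The other is whether the AE tables and task-satisfaction summaries describe the population that Protocol 5.6 says they describe.

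**Working it through.** **Step 1. Apply each rule to two kinds of subject, neither with a vessel attempt.**

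| Rule | X1 used for cutting or dissection | X1 used only for grasping, adhesiolysis or bundle division |
|---|---|---|
| Protocol 3.1: enrolled? | No | No |
| Protocol 3.2.2: pages | AE yes, Usage no | AE yes, Usage no |
| Protocol 3.1: day-28 follow-up promised? | No | No |
| Protocol 5.6: in the performance and safety set? | Yes | Yes |
| SAP 6: in the ENSEAL Analysis Set? | Yes in principle, but the answer is not collected | No |
| SAP 8.7: summarised? | No | No |
| SAP Listing 24: recorded AE listed? | Yes | Yes |

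Protocol 5.6 includes both subjects, and SAP 8.7 excludes both. SAP 6 separates them, by way of a page that Protocol 3.2.2 does not have completed.

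**Step 2. Reproduce the plan's safety figures (Protocol 5.7, n = 105, incidence 2%).**
- Chance of at least one event: 1 − 0.98^105 = 88.0%, as stated.
- Exact two-sided 95% upper limit for 0/105: 1 − 0.025^(1/105) = 3.45%, in line with the stated figure of less than 3.5%.

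Neither figure is disputed.

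**Step 3. Size.** The documents do not give the number k of exposed subjects without a vessel attempt, so k is an assumption. Among k subjects at the protocol's 2% example rate, the chance of at least one event is 1 − 0.98^k and the expected number is 0.02k. The last two columns show the Step 2 figures if these subjects were also followed, so that n = 105 + k.

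| k | Chance of ≥1 event among the k | Expected events | Chance of ≥1 event at n = 105 + k | Upper limit for 0 events |
|---|---|---|---|---|
| 0 | 0 | 0 | 88.0% | 3.45% |
| 5 | 9.6% | 0.1 | 89.2% | 3.30% |
| 10 | 18.3% | 0.2 | 90.2% | 3.16% |
| 20 | 33.2% | 0.4 | 92.0% | 2.91% |

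Only events that the site does not otherwise learn of would go unrecorded, so the second and third columns are upper bounds on what is missed at this rate.

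**Step 4. Direction.**
- *Subjects omitted.* They leave both numerator and denominator. The reported rate is then too low only if their risk exceeds that of enrolled subjects, and too high if it is lower. The documents give no data on this.
- *Subjects counted without follow-up.* Assume 5 subjects with a device-related AE among 105, and 15 added subjects with none observed. The rate falls from 5/105 = 4.8% to 5/120 = 4.2%. At equal risk, 15 × 4.8% = 0.7 event subjects would be expected among the 15. With 1 to 3 added subjects the rate is 5/106 = 4.7% to 5/108 = 4.6%. For scale, the exact 95% interval for 5/105 is 1.6% to 10.8%. Both the 5 and the 15 are illustrative.

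**The case against.** A reader might infer that exposed patients escape safety follow-up altogether. The documents do not support that. Protocol 3.2.2 itself keeps the AE page. Protocol 6.4.1 has the investigator record every attributable AE and collect data until it resolves or stabilises. Protocol 7.1.1 requires an AE form when a product complaint concerns a safety event, and Listing 24 covers all subjects. No text says that a screen failure is not seen at Visit 3; this is inferred from Protocol 3.1 and 3.2.2.

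A reader might also infer that the AE rate is biased downward. That does not follow either. Omission has no known direction. Dilution needs a site to complete a form that Protocol 3.2.2 does not call for, and it needs SAP 8.7 to be disregarded.

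It can further be said that a vessel-attempt trigger is used consistently in Protocol 3.1, 3.2.1 and 3.2.2 and suits a vessel-level primary endpoint. Inclusion criterion 1 requires a planned X1 vessel transection, and Protocol 5.7 expects at least one transection per procedure, so few subjects may be affected.

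All of this stands, but it does not remove the conflict. An AE page is a place to record an event, not a scheduled enquiry. The Schedule of Events places AE assessment at Visits 2 and 3 and at unscheduled visits, and it allows completion to be recorded at Visit 2. For subjects who withdraw, Protocol 3.2.5 asks for every effort to obtain final-visit observations; nothing comparable is written for exposed screen failures. Table 1 shows that failure during surgery was foreseen, although that row may also hold subjects in whom X1 was never used. The vessel-attempt trigger can stay. The fault is that the data-collection rule and the analysis-set rules do not match.

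**Conclusion.** The point holds as an inconsistency among Protocol 3.2.2, Protocol 5.6, SAP 6 and SAP 8.7. Followed as written, subjects exposed to X1 without a vessel attempt have no guaranteed discharge or day-28 AE ascertainment. They drop out of the AE tables and the task-satisfaction summaries, and any AE recorded for them appears only in a listing.

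This rests on three readings: that the page list in Protocol 3.2.2 is exhaustive, that follow-up promised to enrolled subjects is not extended to others, and that SAP 8.7 governs where it conflicts with SAP 6.

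The size cannot be fixed from the documents: with no such subjects there is no effect, and Step 3 gives the range for assumed numbers. The vessel-level primary endpoint and the sample-size figures are untouched. The correction is worth making because it is cheap and makes the safety set match its own definition.

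**What to change.** - **Protocol 3.2.2.** For a consented subject with any X1 use on tissue but no vessel attempt, complete the existing Usage, intra-operative and discharge pages as well as the AE page, and carry out the Visit 3 contact. Subjects with no X1 use remain screen failures.
- **Counting.** Keep these subjects out of the vessel endpoint and out of the target of 35 to 40 per procedure group.
- **SAP 6.** Let any recorded X1 use qualify for the ENSEAL Analysis Set, not only cutting or dissection.
- **SAP 8.7.** Base summaries on the ENSEAL Analysis Set rather than on enrolled subjects only, so that these subjects count in the AE tables and task-satisfaction summaries as Protocol 5.6 states.

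The Protocol and SAP changes are needed together. Changing 3.2.2 alone leaves SAP 8.7 excluding these subjects and SAP 6 missing those with grasping, adhesiolysis or bundle division only.

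The cost is the amendment wording, a few extra eCRF pages and one contact, which the Schedule of Events already allows by telephone, for what is probably a small number of subjects.
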